After Randomisation, Part 1 (Acute Exacerbation Phase) of the study continues with daily evaluation up to Day 7. Further evaluations will be performed on Days 10 and 14. Subjects will receive their first dose of study treatment within a maximum of 24 hours after presenting with an acute exacerbation (Day 1). Subjects will be eligible only if their treatment (SoC) has been initiated less than 24 hours before Randomisation and dosing. Study treatment will be administered on Days 1, 3 and 5. Subjects will undergo all safety and efficacy assessments on Day 1. Physical examinations, 12-lead ECGs, pulmonary function test (PFT; spirometry), and blood sampling for blood biomarkers will be done every day during the Acute Exacerbation Phase (Days 1 to 7, Day 10 and Day 14). It is expected that subjects will be hospitalised during Part 1 (Day 1 - Day 7). However, if a subject improves and is discharged prior to Day 7, the subject should return to the facility daily through to Day 7 and on Days 10 and 14 for completion of study assessments. Upon discharge the subject will be given a diary to document any occurrences of COPD and rescue medication use.

Part 2 (Stabilisation Phase) of the study requires subject evaluations at Weeks 8, 12 and 26. During Part 2 of the study, the subject's medical condition will be monitored at each visit and SoC medication adjusted as needed.

[figure not shown]
The End of Study is defined as the last visit of the last global subject.

Subjects will undergo sparse PK sampling (4 samples collected on any 2 of the 3 treatment days).

This study does not restrict the appropriate care of the subject and allows the use of the current institution SoC with respect to dose, regimens, duration of treatment for medical treatment of the subject. In agreement with the updated version of GOLD (2015) for the treatment of acute exacerbations of COPD, subjects must be receiving at least steroids and/or antibiotics. However medications that may interfere with metabolism of the study drug or that may bring additional risk to the subject should be avoided. These medications are referred as prohibited concomitant medications (Table 10-1) and are exclusionary from the study.

A study schematic is provided in (Figure 9-1).

Figure 9-1: Schematic of Study Design

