9.1.3.2 Day 1 to Day 14 – Acute Exacerbation Phase

All subjects will initially be hospitalised. However, if a subject improves and is discharged prior to Day 7, the subject should return to the study facility daily up to and including Day 7 for study drug administration and completion of study assessments.

The subject should receive a diary on Day 1 after Randomisation and be instructed in its use. Prior to hospital discharge, the subject should be reminded about the use of the diary and need to bring their diary to all visits.

Study Day 1, Visit 1 (prior to study drug administration)

Once Screening has been completed, the following assessments/procedures will be done for all subjects:

1. Concomitant medication
2. If the Screening visit and Day 1 are performed on different days, the following assessments should be repeated at Day 1 prior to Randomisation only if the subject's condition has deteriorated:
 - Physical examination, including vital signs (body temperature, RR, pulse rate, blood oxygen [measured using a pulse oximeter], systolic and diastolic blood pressure) and weight
 - Blood sample for clinical laboratory tests (haematology and biochemistry) to be taken at least 6 hours after SABA (whenever possible; times of sample collection and SABA intake must be recorded), after 8 hours of fasting (wherever possible), and after completion of ECG and vital signs (body temperature, RR, pulse rate, systolic and diastolic blood pressure). These clinical laboratory tests will be performed at both the local and central laboratory to confirm eligibility for Randomisation
 - Urinalysis (specific gravity, pH, protein, glucose, blood)
3. 12-lead ECG; recorded after 10 minutes at rest
4. Randomisation via IRT to allocate subjects to a treatment group. All necessary data for completing the IRT system, per IRT manual, should be available
5. Chronic respiratory questionnaire (CRQ); Visit 1 questionnaire will be considered the Baseline score
6. Collection of mMRC dyspnoea scale

7. Blood sample for clinical laboratory tests (inflammatory blood biomarkers) to be taken at least 6 hours after SABA (whenever possible; times of sample collection and SABA intake must be recorded), after 8 hours of fasting (not essential if this is the initial visit), and after completion of ECG and vital signs (body temperature, RR, pulse rate, blood oxygen [measured using a pulse oximeter], systolic and diastolic blood pressure)

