13.4.3 Exploratory Endpoints(s)

The following data were collected as exploratory endpoints:

1. Exploratory composite scale comparing the following among the three groups at Week 8, 12 and 26:
 - Number of events of worsening symptoms warranting the addition of antibiotics
 - Number of events of worsening symptoms warranting an increase in dose of oral corticosteroids or initiation of new oral corticosteroids
 - Number of events of worsening symptoms requiring additional treatment of oral corticosteroids and/or antibiotics after completion of the initial regimen
 - Number of events of COPD exacerbation requiring re-hospitalisation
 - Number of COPD-related deaths.
2. Change in CRQ from Baseline at Day 14 and Weeks 8, 12 and 26 to evaluate recovery, comparing among the three groups over time
3. Cumulative oral/IV steroid dose from Day 1 to Day 14, and from Day 14 to Week 26
4. Change in inflammatory blood biomarkers (IL-6, TNF- α , fibrinogen, hs-CRP, and MPO) daily during Part 1 of the study, and at Weeks 8, 12 and 26
5. Relationship between BCT197 exposure and efficacy/safety endpoints
6. Change from Baseline in mMRC overtime
7. BODE index among the three groups at Day 14.

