13.5 Description of Statistical Analyses

13.5.1 General Considerations

The statistical evaluation will be performed by ICON using SAS®, Version 9.3 or later. Data will be analysed by either enumeration of subjects displaying distinctive characteristics within each treatment regimen or by descriptive statistical summaries such as means, SD, medians, and ranges for continuous measures. Categorical variables will be presented by the number of observations and absolute and relative (%) frequency.

For efficacy data, summary statistics (N, mean, SD, median minimum and maximum for continuous data, and N [%] for categorical data) will be presented at each visit.

Similarly, changes from Baseline (or percentage change from Baseline if appropriate) will be summarised in a similar manner.

The main population for efficacy analysis will be the ITT population.

Unless stated otherwise, the Baseline value for a variable will be the latest value taken prior to the first dose of study medication.

Data in summary tables will generally be presented on an Observed Cases basis.

Unless stated otherwise, all statistical tests will be two-sided and conducted at the 5% level, and all quoted confidence intervals will be two-sided 95% confidence intervals. All three treatment regimens will be assessed by pairwise comparisons, no adjustment for multiplicity will be made and all analyses will be considered as exploratory analyses.

Full details of the statistical analysis will be given in the SAP.

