8.1.5 Definitions of Baseline

The efficacy/exploratory endpoints to be analysed separately during the Acute Exacerbation Phase and the Stabilisation Phase are the EXACT-PRO total score and subscores (and exacerbation parameters derived from EXACT-PRO), the change from baseline in CRQ over time and the change from baseline in mMRC dyspnoea scale over time.

For summary purposes, the baseline value for Acute Exacerbation Phase will be defined as the last non-missing value collected prior to the first dose of study medication, unless other specified. Moreover, for the efficacy/exploratory endpoints to be analysed separately during the Acute Exacerbation Phase (from Study Day 1 until Day 14) and the Stabilisation Phase (from Day 14 until Week 26), the baseline value for Stabilisation Phase will be defined as the value collected on Visit 9 (Day 14), unless other specified. For Stabilisation Phase, no value available prior to Visit 9 (Day 14) will be used for definition of baseline, as the patient might not yet be under stable condition for COPD prior to Day 14.

For EXACT-PRO, as there is no stable period during which EXACT-PRO scores are collected prior to administering the study drug, the definition of the Baseline EXACT-PRO from the user manual⁶ will not be used for Acute Exacerbation Phase. The score and subscores obtained on Day 1 of the EXACT-PRO observation period, which corresponds to Study Day 1, will be used as the baseline for Acute Exacerbation Phase. Moreover, the Baseline EXACT-PRO score (or subscores) for Stabilisation Phase will be defined as the mean EXACT score during the first 7 days of the Stabilisation Phase (Week 3; Days 15-21), with a minimum of 4 days of available data required to compute the baseline value. If 4 or more of the first 7 days of data are not available, the baseline EXACT-PRO score for Stabilisation Phase will not be calculated.

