For the following study periods: [0-4) weeks, [4-8) weeks, [8-12) weeks, [12-16) weeks, [16-20) weeks and [20-26) weeks, the number of clinical treatment failure-free patients at the beginning of the period, the cumulative number of patients with CTF at the end of the period and the probability of having experienced a CTF at the end of the period with the associated two-sided 95% CIs will be presented by treatment regimen. The point estimates and the relative two-sided 95% CIs will be presented by treatment regimen for the 75th, 50th and 25th percentiles. A Kaplan-Meier plot will also be presented. Comparisons between treatment regimens will be performed by means of the log-rank test. The p-values of the pairwise log-rank test comparisons will be displayed on the figure.

8.6.4.2 Change in CRQ from Baseline at Day 14 and Weeks 8, 12 and 26

This exploratory endpoint will be analysed separately during the Acute Exacerbation Phase (from Study Day 1 until Day 14 included) and the Stabilisation Phase (from Day 14 until Week 26).

The CRQ total score and domain scores will be summarised at each visit by treatment group using descriptive statistics. Changes in CRQ from baseline (Visit 1 pre-dose) will be summarised at Day 14 during the Acute Exacerbation Phase by treatment regimen. Changes in CRQ from baseline (Visit 9, Day 14) will also be summarised at each post-baseline visit (Weeks 8, 12 and 26) during the Stabilisation Phase by treatment regimen.

Change in CRQ total score from baseline (Visit 1 pre-dose) to Day 14 (Acute Exacerbation Phase) will be analysed using an ANCOVA model estimating the effect at Day 14, using OC, including treatment, severity of airflow limitation at baseline (pre-dose), blood eosinophils (%) value at baseline (pre-dose), time from start of current COPD exacerbation to first IMP dosing, presence of cardiovascular comorbidities at screening and COPD exacerbation treatment at screening as fixed effects and baseline CRQ total score (Visit 1 pre-dose) as a covariate.

The ANCOVA model results will be presented with LSMEAN and standard error (SE) of each treatment regimen as well as the adjusted mean difference between treatment regimens at Day 14 and associated two-sided 95% CIs. Each pairwise treatment regimen comparison will be tested at an alpha level of 5%. P-values of the effects will also be presented.

A similar ANCOVA analysis as above will be performed for each of the 3 CRQ domain scores during the Acute Exacerbation Phase.

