MMRM analysis using an unstructured covariance matrix and the Kenward-Roger adjustment for the denominator degrees of freedom will be performed for statistical comparison of treatment regimens during the Stabilisation Phase with change in CRQ total score as an outcome. Model will consider treatment, severity of airflow limitation at baseline (pre-dose), blood eosinophils (%) value at baseline (pre-dose), time from start of current COPD exacerbation to first IMP dosing, presence of cardiovascular comorbidities at screening and COPD exacerbation treatment at screening as fixed effects and baseline CRQ total score (Visit 9/Day 14) as covariate. In addition the baseline CRQ total score-by-visit and the treatment-by-visit interactions will be included in the model.

LSMEAN and standard error (SE) of each treatment regimen, difference of LSMEANS between treatment regimens and their associated two-sided 95% CIs and corresponding two-sided P-values for Weeks 8, 12 and 26 (Stabilisation Phase) will be estimated by the model. P-values of the effects will also be presented.

The unstructured covariance matrix (which does not presume a particular correlation structure for repeated measurements within patients over time) will be used to adjust for the within-patient error variance covariance. In case model fails to converge, other covariance matrix structures will be considered in the sequence of Ante-dependence, Toeplitz, Heterogeneous AR(1), Heterogeneous Compound Symmetry, and Compound Symmetry.

A similar MMRM analysis as above will be performed for each of the 3 CRQ domain scores during the Stabilisation Phase.

A figure with adjusted mean change from baseline (Visit 9/Day 14) in CRQ total score and domain scores at each visit during the Stabilisation Phase by treatment regimen derived from the linear mixed model will also be provided for each score.

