8.6.4.5 Change from Baseline in mMRC dyspnoea scale over time

This exploratory endpoint will be analysed separately during the Acute Exacerbation Phase (from Study Day 1 until Day 14 included) and the Stabilisation Phase (from Day 14 until Week 26).

The mMRC dyspnoea scale (graded from 0 to 4) will be summarised at each visit by treatment regimen using descriptive statistics. Changes in mMRC dyspnoea scale from baseline (Visit 1 pre-dose) will be summarised at each post-baseline visit (Day 7 and Day 14) during the Acute Exacerbation Phase by treatment regimen. Changes in mMRC dyspnoea scale from baseline (Visit 9, Day 14) will also be summarised at each post-baseline visit (Weeks 8, 12 and 26) during the Stabilisation Phase by treatment regimen.

MMRM analysis using an unstructured covariance matrix and the Kenward-Roger adjustment for the denominator degrees of freedom will be performed for statistical comparison of treatment regimens with change in mMRC as an outcome. MMRM analyses will be done separately for the Acute Exacerbation Phase and for the Stabilisation Phase. Both models will consider treatment, severity of airflow limitation at baseline (pre-dose), blood eosinophils (%) value at baseline (pre-dose), time from start of current COPD exacerbation to first IMP dosing, presence of cardiovascular comorbidities at screening and COPD exacerbation treatment at screening as fixed effects and baseline mMRC (Visit 1 pre-dose for the Acute Exacerbation Phase, Visit 9/Day 14 for the Stabilisation Phase) as covariate. In addition the baseline mMRC-by-visit and the treatment-by-

visit interactions will be included in the model.

LSMEAN and standard error (SE) of each treatment regimen, difference of LSMEANS between treatment regimens and their associated two-sided 95% CIs and corresponding two-sided P-values for Day 7, Day 14 (Acute Exacerbation Phase) and Weeks 8, 12 and 26 (Stabilisation Phase) will be estimated by the model. P-values of the effects will also be presented.

The unstructured covariance matrix (which does not presume a particular correlation structure for repeated measurements within patients over time) will be used to adjust for the within-patient error variance covariance. In case model fails to converge, other covariance matrix structures will be considered in the sequence of Ante-dependence, Toeplitz, Heterogeneous AR(1), Heterogeneous Compound Symmetry, and Compound Symmetry.

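### Week 8–26 CRQ and mMRC are tested only from a post-treatment Day 14 value, not declared as a change from the protocol, and RR normalisation is judged against each patient's own Week 8–26 mean

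*SAP*

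**What the plan says.** **Protocol.** Section 13.5.1 states that, unless otherwise stated, "the Baseline value for a variable will be the latest value taken prior to the first dose of study medication". Section 9.1.3.2, for Day 1 before dosing, is specific: "Chronic respiratory questionnaire (CRQ); Visit 1 questionnaire will be considered the Baseline score". Section 13.4.3 lists the endpoint "Change in CRQ from Baseline at Day 14 and Weeks 8, 12 and 26 to evaluate recovery, comparing among the three groups over time", and change from Baseline in mMRC over time. Dosing is complete by Day 5 (9.1.1: "Study treatment will be administered on Days 1, 3 and 5"). Section 13.5.3 plans an MMRM of change from Baseline for each continuous secondary parameter.

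**SAP, CRQ and mMRC.** Section 4.3 repeats the protocol endpoints unchanged. Section 8.1.5 splits CRQ and mMRC into two phases; for the later one, "the baseline value for Stabilisation Phase will be defined as the value collected on Visit 9 (Day 14), unless other specified", and no earlier value may serve. The reason given is that patients may not be stable before Day 14. The Week 8–26 MMRMs follow this rule: 8.6.4.2 takes "baseline CRQ total score (Visit 9/Day 14) as covariate", and 8.6.4.5 uses "Visit 9/Day 14 for the Stabilisation Phase) as covariate". Pre-dose values serve only up to Day 14. Raw scores are summarised at every visit.

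**SAP, EXACT-PRO.** After Day 29, change is descriptive only, from a Days 15–21 mean (8.1.5, 8.6.3.10).

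**SAP, RR.** Under 7.1.4.6, RR at Days 1–14 is normalised if it is at or below the patient's own mean at Weeks 8, 12 and 26; one value is enough. If all three are missing, the threshold is 20 breaths/min. Rates are compared between arms at each acute-phase visit (8.6.3.5). Change in RR is descriptive only (8.6.3.6).

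**SAP Section 9** declares three changes: the PP definition, the added PP analyses and the steroid-dose period. Baseline is not among them.

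**The concern.** The protocol has one Baseline for Day 14 and for Weeks 8, 12 and 26. Day 14 is one of the visits at which change from Baseline is to be measured, so it cannot also be that Baseline. It follows all dosing, and the CRQ asks about the previous two weeks (SAP Appendix D), so the Day 14 CRQ covers the whole treatment period. Adjusting for it removes part of any effect already achieved. It also drops patients without a Day 14 score, since SAP Appendix F excludes missing covariates. The comparison is then no longer protected by randomisation.

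The RR rule has the same root. The threshold for an early outcome is measured months after randomisation, so anything that differs between arms late in the trial moves the early result. There is no other between-arm test of RR: the planned MMRM became descriptive, and SAP 8.7 tests no safety data.

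**Working it through.** **The plan's own figure.** For the primary endpoint, n = 2 × (1.96 + 0.8416)² × 230² / 100² = 83.04, so 84 per arm; the t-based solution is 84.01, so 85. Then 255 / 0.95 = 268.4, so 269 against the stated 270 or so. The sample size reproduces and is not in question. It supplies the 85 per arm used below.

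**CRQ and mMRC.** The documents give no effect, SD or correlation for these scales, so all of these are assumed: unit SD, a Day 14 effect d14 = 0.5 SD, Day 14-to-late correlation r = 0.4 / 0.55 / 0.7, and pre-dose correlation 0.3 with both later values.

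- Expected contrast under the SAP model = d_late − r × d14
- SE = √[(2/85)(1 − r²)(1 + d14²/4)]; the last factor arises because the covariate differs between arms
- SE = 0.145 / 0.132 / 0.113 for the three values of r
- Chance of a significant result ≈ Φ(|contrast|/SE − 1.96)

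| True late effect (SD) | SAP contrast, r = 0.4 / 0.55 / 0.7 | Significant under SAP model | Pre-dose model |
|---|---|---|---|
| 0.50 (sustained) | 0.30 / 0.225 / 0.15 | 54% / 40% / 26% | 0.50, about 92% |
| 0.25 (halved) | 0.05 / −0.025 / −0.10 | – | 0.25 |
| 0 (gone) | −0.20 / −0.275 / −0.35 | apparent harm: 28% / 55% / 87% | 0, about 5% |

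Example, r = 0.4 and sustained: 0.5 − 0.4 × 0.5 = 0.30; 0.30 / 0.145 = 2.07; Φ(0.11) = 54%. The pre-dose SE is √[(2/85)(1 − 0.3²)] = 0.146; 0.5 / 0.146 = 3.42; Φ(1.46) is about 93%.

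Simulation (4,000 trials per scenario) gave contrasts of 0.300 / 0.223 / 0.149 for the sustained case, significant in 54.2 / 39.6 / 26.4%. For the vanished effect, apparent harm was significant in 28.6 / 54.3 / 86.1%, against 4.4–5.9% significant under the pre-dose model. With no Day 14 effect and a late effect of 0.5, the SAP model recovered 0.496–0.499, so it is then unbiased.

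**RR normalisation.** Assumed: between-patient SD 1.5, within-patient SD w = 1.5 / 2.0 / 2.5, acute RR 2/min above habitual, whole-number readings. Let D be acute RR minus the mean of three late values; the between-patient part cancels.

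- Mean of D = 2 + early effect − late effect
- SD of D = √[(w² + 1/12) × 4/3] = 1.764 / 2.333 / 2.906
- A tie counts as normalised and D moves in thirds, so pass rate ≈ Φ((1/6 − mean)/SD)

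| Effect on RR (per min) | Mean of D | Pass rate, w = 1.5 / 2.0 / 2.5 |
|---|---|---|
| none | 2.0 | 15 / 22 / 26% |
| −1 early only | 1.0 | 32 / 36 / 39% |
| −1 early and late | 2.0 | 15 / 22 / 26% (cancels) |
| −0.5 early, −1 late | 2.5 | 9 / 16 / 21% (reverses) |

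These agree with simulation of 400,000 patients per cell. A fixed 20/min rule does show the equal −1 effect: 57–59% rises to 70–76% at a habitual mean of 18, and 5–12% rises to 12–20% at 22.

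**The 20/min fallback.** A recovered patient passes 80–88% of the time at habitual mean 18, 57–59% at 20, 41–43% at 21 and 24–30% at 22, against 52–54% on the own-plateau rule. If the planned 5% drop-out all used the fallback, the largest shift for recovered patients would be 0.05 × (88 − 54) = 1.7 points. This part is minor.

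**The case against.** CRQ and mMRC are exploratory, the study is described as hypothesis-generating, and raw scores are summarised at each visit. A sustained benefit would therefore show as separated arm means, and it is also tested without this bias at Day 14 (mMRC at Day 7 too). The Day 14 rule is stated openly in SAP 8.1.5 with a reason, and Protocol 13.5.1 permits exceptions. These points limit the weight. They do not supply a valid late test, and nothing is concealed: the gap is that Section 9 is silent although the protocol names the Visit 1 CRQ as Baseline.

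On RR, the protocol gives no normalisation threshold, so the own-plateau rule fills a gap; the fault is in the definition, not a departure. Comparing patients with their own recovered state is clinically sensible, and no stable pre-study RR is scheduled. An early-only benefit is preserved. Cancellation or reversal needs late RR to differ between arms, and SAP Appendix A does not expect drug in the body by Week 8. That is fair, but drug need not be present. Protocol 9.2 aims for fewer relapses, and SAP 7.1.4.6 does not exclude RR taken during a new exacerbation; Protocol 7.1 cites about 32% of exacerbations occurring within 8 weeks of a preceding one. If one of three late values is raised by 2/min (assumed), the threshold rises by 2/3 and the no-effect pass rate goes from 15–26% to 25–34%. An arm with more relapses would look more normalised.

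The magnitudes are assumed, and 87% is an extreme: full loss of a 0.5 SD effect at r = 0.7. mMRC is a 0–4 grade treated here as continuous, as the SAP's own MMRM does. The EXACT-PRO point involves no biased test, only an untested late period.

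**Conclusion.** The concern holds and should be fixed. For any positive correlation and any Day 14 benefit, the Week 8–26 CRQ and mMRC models understate the late effect. Over the assumed range they recover 30–60% of a sustained 0.5 SD effect (0.15/0.5 to 0.30/0.5), and an effect that wanes can appear as harm. With no Day 14 effect there is no bias. The change of baseline is not declared in Section 9.

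The RR rule keeps an early-only benefit, cancels an equal early and late one, and reverses when the late benefit is larger. RR has no between-arm test free of that threshold.

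The direction follows from the definitions; the sizes rest on assumed correlations, SDs and effects. Not affected: the primary endpoint, sample size, spirometry normalisation, biomarkers, treatment failure, and the early tests of CRQ (Day 14), mMRC (Days 7 and 14) and EXACT-PRO (to Day 29).

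**What to change.** - **CRQ and mMRC:** fit each as an MMRM of change from the Visit 1 pre-dose value at all post-baseline visits to Week 26, adjusted for that value. Keep change from Day 14 as descriptive.
- **EXACT-PRO:** add change from Day 1 through Week 26. Keep the Days 15–21 baseline for detecting EXACT events.
- **RR:** base the between-arm test on a rule that uses no post-randomisation threshold. The protocol's MMRM of RR change from pre-dose Baseline is preferable because it needs no cut-off. The 20 breaths/min already in the SAP, applied to everyone, is the alternative, but it misclassifies patients whose habitual RR is high. Keep the own-plateau rate as descriptive.
- **Section 9:** declare any departure that remains.

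The cost is SAP wording and re-specified models on data already scheduled; no visits or patients are added, and every summary now planned can be retained.
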